5. HYPOTHESES AND/OR ESTIMATION

The incidence of RBC transfusions in each treatment group (Hb-based titration group and fixed dose group) and their difference will be estimated, and no formal hypothesis will be tested. The width of the 95% CI of the transfusion incidence rate is expected to be < 10% (ie, $\pm 5\%$ around the point estimate) in each group and the width of the 95% CI of the difference in transfusion incidence rates is expected to be < 14% (ie, $\pm 7\%$ around the point estimate). The efficacy and safety of each treatment group will be described, as these aspects will assist in the determination of a preferred dosing regimen.

6. DEFINITIONS

6.1 Study Time Points

Informed Consent Date

The informed consent date for each subject is the date the subject signs the original informed consent for this study.

Enrolled

Individuals are considered enrolled if they have been assigned a randomization number and have a non-missing randomization date. Enrolled individuals are referred to as "subjects".

Randomization (Enrollment) Date

The randomization date for each subject is the date the investigator (or designee) confirms in the IVRS that the subject has met all eligibility criteria and is randomized.

Study Day 1

Per protocol, all subjects must receive the first dose of investigational product on the date of randomization. Therefore, for each subject, Study Day 1 will be defined as the day of randomization.

Study Day

For each subject and for a given study visit date, study day is defined as the number of days since Study Day 1:

$$\text{Study day} = (\text{study visit date} - \text{Study Day 1 date}) + 1$$

If the date of interest is prior to the Study Day 1:

$$\text{Study day} = (\text{study visit date} - \text{Study Day 1 date}).$$

Date of Last Dose of Investigational Product Received

For each subject, the date of last dose of investigational product received is defined as the date of last administration of the investigational product during the study.

End of Investigational Product (EOIP) Date

For each subject, the end of investigational product date is defined as the date recorded on the End of Investigational Product Electronic Case Report Form (eCRF).

End of Study (EOS) Date

For each subject, the end of study date is the date recorded on the End of Study eCRF.

Study End Date

The study end date is the last end of study date of all randomized subjects.

Study Month

One study month is defined as 4 weeks (28 days)

Last Known Date

Defined as the last available complete date in the clinical database for a subject, eg, date a scheduled measurement is taken or an investigational product is administered, concomitant date, adverse event date, end of study date, reported endpoint onset date, etc.

6.2 Demographics and Baseline Related Definitions

Age

Age will be calculated as the subject's (floor) integer age in years at the randomization date.

Screening Weight

Weight measured at the first screening visit, which the starting dose is calculated upon.

Baseline Hb Value

The baseline Hb value is defined as the mean of the 2 most recent non-missing Hb concentrations measured through the Hemocue device prior to or on the randomization date. If for any reason only 1 value is available, then that value will be used as baseline.

Baseline Values (other than Hb)

The baseline value is the last non-missing value measured prior to or on the randomization date.

Baseline Body Mass Index

The baseline body mass index (BMI) is calculated as [baseline weight (kg) / baseline height (m)²].

Change from Baseline

The arithmetic difference between a post-baseline value and baseline value for a given time point:

$$\text{Change from baseline} = (\text{post-baseline value} - \text{baseline value})$$

Percent Change from Baseline

The percent change from baseline for a given variable at a given time point is defined as:

$$100 \times [(\text{value at given time point} - \text{baseline value}) / \text{baseline value}]$$

Estimated Glomerular Filtration Rate

Estimated glomerular filtration rate (eGFR, mL/min/1.73m²) will be calculated using Chronic Kidney Disease Epidemiology Collaboration (CKD-EPI) equation

(Levey et al, 2009):

$$\text{eGFR} = 141 \times \min(\text{Scr}/\kappa, 1)^\alpha \times \max(\text{Scr}/\kappa, 1)^{-1.209} \times 0.993^{\text{Age}} \times 1.018 \text{ [if female]} \times 1.159 \text{ [if black]}$$

Where Scr is serum creatinine (mg/dL), κ is 0.7 for females and 0.9 for males, age is the age at the time the measurement is taken, α is -0.329 for females and -0.411 for males, min indicates the minimum of Scr/ κ or 1, and max indicates the maximum of Scr/ κ or 1.

Stratification Factors

- RBC transfusion received within 12 months prior to randomization: Yes, No
- Site practice setting: Nephrology, Non-nephrology, pre-specified by the specialty of the principal investigator at the time of site initiation

Baseline Subgroups

- Age: < 65, ≥ 65 and < 75, ≥ 75 years
- Gender: Female, Male
- Race: White, Black, Other
- Baseline Hb concentrations: < 9.0, ≥ 9.0 – < 9.5, ≥ 9.5 – < 10.0 g/dL
- Baseline eGFR: < 30.0, ≥ 30.0 mL/min/1.73m²
- Diabetes at baseline: Yes, No

6.3 Other Study Related Definitions

Analytical Window Assignments

Analytical windows will be used to summarize protocol specified parameters according to the protocol schedule. This algorithm is provided in [Appendix A](#).

Analytical Window Assignments

Analytical windows will be used to summarize protocol specified parameters according to the protocol schedule.

Exposure to Investigational Product

For each subject who received at least one dose of IP, the number of days of IP exposure Period is calculated as [(Date of Last Dose of Investigational Product Received – first dose date + 1) + 28 days]. The exposure to IP in study month = exposure to IP / 28 days.

Study Exposure

For each randomized subject, study exposure is defined as time from the randomization date to the end of study date.

Evaluation Periods for Different Analysis Approaches

The evaluation period of the on-treatment approach begins from the date of randomization, and subjects will be censored at the last dose of investigational product plus 3 months or end of study, whichever is earlier.

The evaluation period of the on-study approach begins at the date of randomization and subjects will be censored at the end of study date.

Treatment Emergent Adverse Events

Treatment emergent adverse events are adverse events occurring on or after the first dose of IP.

Adverse Events of Special Interest

Adverse events falling into categories of special interest (EOI) will be reported according to the special interest category. The categories of interest for the study are:

- Hypertension
- Ischemic Heart Disease
- Cardiac Failure
- Cerebrovascular Disorders
- Dialysis Vascular Access Thrombosis
- Embolic and Thrombotic Events (including arterial thromboembolic events, venous thromboembolic events and vessel type unspecified and mixed arterial and venous)
- Convulsions
- Antibody-Mediated Pure Red Cell Aplasia (PRCA)
- Hypersensitivity
- Lack of Efficacy-Effect
- Malignancies

The definition of each EOI may be modified and a new EOI may be added based on findings from ongoing pharmacovigilance. Updates of the search strategy due to MedDRA upgrades or other reasons may not trigger a SAP amendment. However, the most recent EOIs per Amgen EOI search strategy will be used at the time of the analysis and these search terms will be included in an appendix of the study report.

Adverse Event Subject Incidence

Defined as the number and percentage of subjects with a reported event(s). For subjects with multiple reports of the same event during the study, the subject will be counted only once. If a pre-existing condition worsens on or after the first dose of investigational product administered, the event will be counted as if it occurred on the day it worsened. For adverse event tabulations involving relationship to investigational product, the subject is counted in the tabulations if at least 1 occurrence of the event is

related. For adverse event tabulations involving severity, the highest severity of the particular adverse event will be used for each subject.

Hemoglobin

For all Hb-related endpoints, the Hb measured using the point of care device will be used. For Hb measured by the central laboratory, they will only be summarized descriptively by treatment group at each scheduled visit.

Achieved Hb Concentration while Receiving Investigational Product

For each subject, the achieved Hb concentration while receiving IP will be derived using the area under the curve (AUC) method with all Hb measured during the period starting from Week 13 (Study Day 85) to the last dose date will be included in the calculation. The 12 week interval is indicated in the USPI as escalation period.

Post-baseline Hb Concentration Subgroup

Post-baseline Hb concentration subgroup is defined as < 8.0, ≥ 8.0 and < 9.0, ≥ 9.0 and < 9.5, ≥ 9.5 and < 10.0, ≥ 10.0 and ≤ 10.5, > 10.5 and ≤ 11.0, > 11.0 and ≤ 12.0, > 12.0 and ≤ 13.0, > 13.0 g/dL

Hb Rate of Change (ROC)

Only Hb measured on and after Study Day 1 and while the subject is receiving the investigational product will be included in the calculation.

ROC (g/dL per 4 weeks) is calculated using the following equation:

$$\text{ROC (g/dL/4weeks)} = [(\text{Hb at visit X} - \text{Hb at Visit Y}) / (\text{Date of Visit X} - \text{Date of Visit Y})] * 28, \text{ where X and Y are consecutive post-baseline visits.}$$

Time to Reach Hb ≥ 10.0 g/dL

Time from the Study Day 1 to the date the Hb measurement reached ≥ 10.0 g/dL for the first time. Subjects who never reach Hb ≥ 10.0 g/dL will be censored on the last date of IP.

Proportion of Hb measurements ≥ 10.0 g/dL

Proportion of Hb measurements ≥ 10.0 g/dL = the number of Hb measurements ≥ 10.0 g/dL / Total number of Hb measurements. Only Hb measured on or after Study Day 1 and while the subject is receiving the investigational product will be included in the calculation.

Hb variability

At any study visit, the Hb variability is the intra-subject Hb standard deviation over the prior 6 months. The Hb variability will be calculated at each scheduled visit from Week 25.

Initial Hb Response

Initial Hb response is defined as the change of Hb concentration from baseline at Week 5.

Initial Hb Response Subgroup

Initial Hb response subgroups are defined as the initial Hb response quartiles based on the initial Hb response analysis set subjects ([Section 7.3](#)) from both treatment groups.

Dose

The dose referred in this analysis plan is the darbepoetin alfa dose from the IP administration. The dose from a placebo injection equals zero darbepoetin alfa dose.

Weight-based Dose at Specific Study Visit

The weight-based dose at any time point = Dose in μg at specific study visit / subject's screening weight in kg.

Cumulative Dose at Specific Study Visit

The cumulative dose at specific study visit = sum of all darbepoetin alfa doses received from Study Day 1 through the specific study visit.

Average Cumulative Dose per 4 Week at Specific Study Visit

Average cumulative dose per 4 week at specific study visit is defined as the 4-week equivalent cumulative dose received at specific study visit.

Average Cumulative Weight-adjusted Dose per 4 Week at Specific Study Visit

Average cumulative weight-adjusted dose per 4 week at specific study visit = average cumulative dose per 4 week at specific study visit / the screening weight in kg.

Transfusion Subgroups

Subjects will be categorized into transfusion subgroups based on the number of transfusion events: No transfusion event, one transfusion event, more than 1 transfusion event.

Transfusion subgroup (on-treatment approach) will be defined using the number of transfusion events where the start date of the transfusion event falls within the evaluation period of the on-treatment approach.

Transfusion subgroup (on-study approach) will be defined using the number of transfusion events where the start date of the transfusion event falls within the evaluation period of the on-study approach.

Time to Event Derivation

For time to event such as time to first transfusion, or time to first major clinical event (eg, major adverse cardiovascular events (MACE), all-cause mortality), time to event is derived from the randomization date to the date of specific event. Subjects that do not experience the event will be censored. For time to event analysis using the on-treatment approach, the censoring date is the last dose date + 3 months (84 days) or the end of study date, whichever is earlier. For time to event analysis using the on-study approach, the censoring date is the end of study date.

Context surrounding RBC Transfusion

Clinical context surrounding RBC transfusion will be collected for each RBC transfusion event, and will be reviewed by an independent Clinical Endpoint Committee (CEC). The clinical context includes the primary reason for the transfusion event, the transfusion setting (eg, dialysis center, intensive care unit, emergency department), Hb at the time of the first transfusion of the transfusion event, clinical events (eg, bleeding, surgery), symptoms and vital signs of concerns.

Total number of units of RBC transfused

The total number of units of RBC transfused using the on-treatment approach is the sum of RBC units transfused between the randomization date and the earlier date of the last dose date + 3 months (84 days) and the end of study date. The total number of units of RBC transfused using the on-study approach is the sum of RBC units transfused between the randomization date and the end of study date.

Number of Days Hospitalized

This is the total number of days of hospitalization between the randomization date and earlier of the date of last IP + 3 months (84 days) and the end of study date for the on-treatment approach; between the randomization date and the end of study date for the on-study approach. Duration of each hospitalization stay is calculated as day of discharge - day of admission + 1. Hospitalizations with identical admission and discharge days will be counted as a hospitalization with duration of 1 day.

Area under the Curve (AUC) Calculation

The AUC is calculated by adding the areas under the graph between each pair of consecutive observations. For measurements y_1 and y_2 at times t_1 and t_2 , the AUC between these 2 times is the product of the time difference and the average of the 2 measurements $(t_2-t_1)*(y_1+y_2)/2$ (Matthews et al, 1990). This is referred to as the trapezoidal method. For $n+1$ measurements y_i at times t_i ($i = 0, \dots, n$),

$$AUC = \frac{1}{2} \sum_{i=0}^{n-1} (t_{i+1} - t_i)(y_i + y_{i+1})$$

Average AUC is AUC divided by the time (day).

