9.1.2 Reporting Procedures for Adverse Events

The investigator is responsible for ensuring that all adverse events observed by the investigator or reported by the subject that occur after randomization through 4 weeks after the last dose of investigational product are reported using the applicable eCRF (eg, Adverse Event Summary eCRF).

The investigator must assign the following adverse event attributes:

- Adverse event diagnosis or syndrome(s), if known (if not known, signs or symptoms),
- Dates of onset and resolution,
- Severity [and/or toxicity per protocol],
- Assessment of relatedness to darbepoetin alfa, and
- Action taken

The adverse event toxicity grading scale used will be the Amgen adverse event standard grading score. The toxicity grading scale used in this study is described in [Appendix B](#).

The investigator must assess whether the adverse event is possibly related to darbepoetin alfa. This relationship is indicated by a "yes" or "no" response to the question: Is there a reasonable possibility that the event may have been caused by darbepoetin alfa?

The investigator must assess whether the adverse event is possibly related to a device. This relationship is indicated by a "yes" or "no" response to the question: Is there a reasonable possibility that the event may have been caused by a device?

The investigator must assess whether the serious adverse event is possibly related to any study-mandated screening procedure. This relationship is indicated by a “yes” or “no” response to the question: “Is there a reasonable possibility that the event may be related to screening procedures?”

The investigator must assess whether the adverse event is possibly related to any study-mandated activity or procedure. This relationship is indicated by a “yes” or “no” response to the question: “Is there a reasonable possibility that the event may have been caused by a study activity/procedure?”

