9.2.2 Reporting Procedures for Serious Adverse Events

The investigator is responsible for ensuring that all serious adverse events observed by the investigator or reported by the subject that occur after signing of the informed consent through 4 weeks after the last dose of investigational product are recorded in the subject’s medical record and are submitted to Amgen. Any serious adverse events with a fatal outcome (regardless of possible relationship to investigational product) occurring through the end of the subject’s participation on the study are to be reported to Amgen. This would include subjects who have been removed from investigational product and continued on-study.

After the protocol-required reporting period defined above, the investigator does not need to actively monitor subjects for serious adverse events. However, if the investigator becomes aware of a serious adverse event after this protocol-required reporting period, the investigator will report the event to Amgen within 24 hours following the investigator’s knowledge of the event. Serious adverse events reported outside of the protocol-required reporting period will be captured within the safety database as clinical trial cases for the purposes of expedited reporting.

The serious adverse event must be submitted to Amgen within 24 hours following the investigator’s knowledge of the event via the applicable eCRF. If the electronic data capture (EDC) system is unavailable to the site staff to report the Serious Adverse Event, the information is to be reported to Amgen via an electronic Serious Adverse Event (eSAE) Contingency Report Form within 24 hours of the investigator’s knowledge of the event. See [Appendix C](#) for a sample of the Serious Adverse Event Worksheet/eSAE Contingency Report Form. When the first notification of a Serious Adverse Event is reported to Amgen via the eSAE Contingency Report Form, the data must be entered into the EDC system when the system is again available.

The investigator must assess whether the serious adverse event is possibly related to any study-mandated activity or procedure. This relationship is indicated by a “yes” or “no” response to the question: “Is there a reasonable possibility that the event may have been caused by a study activity/procedure”?

The investigator is expected to follow reported serious adverse events until stabilization or reversibility.

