10.6 Safety Analyses

10.6.1 Adverse Events

The Medical Dictionary for Regulatory Activities (MedDRA) version 15.0 or later will be used to code all adverse events to a system organ class and a preferred term. All adverse event tables will be summarized by the randomized treatment group.

Treatment-emergent adverse events are events with an onset after the administration of the first dose of IP.

The subject incidence of adverse events will be summarized for all treatment-emergent, serious, treatment-related, serious treatment-related, those leading to withdrawal of investigational product, fatal, and special events of interest (EOI). Subject incidence of EOI will also be summarized according to their categories.

Subject incidence of all treatment-emergent, serious, treatment-related, serious treatment-related, those leading to withdrawal of investigational product, and fatal adverse events will be tabulated by system organ class and preferred term in descending order of frequency.

Subject incidence of all treatment-emergent adverse events will be tabulated by system organ class, high level group term, and preferred term. Summaries of treatment-emergent, serious, treatment-related, and serious treatment-related adverse events occurring in at least 5% of the subjects by preferred term in any treatment arm will be provided in descending order of frequency of the Hb-based titration group. Risk difference and its 95% CI of each preferred term of AE and SAE will be tabulated in descending order of the risk difference.

Subgroup analyses for stratification factors, age group, race, gender, baseline Hb, baseline eGFR and diabetes at baseline will be presented by system organ class and preferred term in descending order of frequency.

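### Treatment-emergent has no end date, so tables combining fatal and non-fatal adverse events select late events by outcome in subjects who stop IP early

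*SAP*

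**What the plan says.** **Definition.** SAP 6.3: "Treatment emergent adverse events are adverse events occurring on or after the first dose of IP". SAP 10.6.1: "Treatment-emergent adverse events are events with an onset after the administration of the first dose of IP". Each gives a start and no end, and they differ slightly on whether onset at the moment of first dosing counts. The only date-based exclusion of AEs in the SAP (9.3.3) is for events that began before treatment.

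**Collection.** Protocol 9.1.2 covers adverse events "that occur after randomization through 4 weeks after the last dose of investigational product are reported using the applicable eCRF". Protocol 9.2.2 covers serious adverse events "that occur after signing of the informed consent through 4 weeks after the last dose of investigational product". It then extends reporting of SAEs with a fatal outcome to the end of the subject's participation and adds: "This would include subjects who have been removed from investigational product and continued on-study". Once the required period is over, "the investigator does not need to actively monitor subjects for serious adverse events".

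**Use.** SAP 10.6.1 and 12.1 plan subject-incidence tables for all treatment-emergent, serious, special-interest and fatal events. SAP 10.6.1 also says: "Risk difference and its 95% CI of each preferred term of AE and SAE will be tabulated".

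**The concern.** Protocol 7.1.5 asks subjects who end IP early to keep attending visits. Protocol 8.1 names dialysis as a reason for ending IP, and Protocol 7.2.9 then permits commercial ESAs. Read literally, a fatal event more than a year after the last dose, on dialysis and another ESA, is a treatment-emergent AE and SAE of the randomised arm. Nobody is required to collect a non-fatal event with the same term on the same day.

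A row such as cardiac failure would then add non-fatal events from one period to fatal events from a longer one. Its risk difference and CI would describe neither an on-treatment nor an on-study comparison. Protocol 2.4 and SAP 5 make safety an input to the choice of regimen, so readers will use these rows.

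**Working it through.** **Inputs**
- Treatment 96 weeks plus follow-up 4 weeks (Protocol 3.4.1).
- End-of-study visit at Week 101 (Protocol 7.1.7), planned Day 701 (SAP Appendix A).
- Planned visit days from SAP Appendix A.
- Required non-fatal collection to last dose + 28 days; fatal SAEs to end of participation, taken here as Day 701.

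**Step 1. Reproduce the plan's duration.** 96 + 4 = 100 weeks, and (701 − 1)/7 = 100 weeks. They agree.

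**Step 2. Length of the fatal-only stretch.** With L the day of the last dose, stretch = 701 − min(L + 28, 701).

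| Last dose | L | Non-fatal collection ends | Fatal collection ends | Fatal-only days |
|---|---|---|---|---|
| Week 1 | 1 | 29 | 701 | 672 |
| Week 25 | 169 | 197 | 701 | 504 |
| Week 49 | 337 | 365 | 701 | 336 |
| Week 73 | 505 | 533 | 701 | 168 |
| Week 93 | 645 | 673 | 701 | 28 |
| Week 97 (completer) | 673 | 701 | 701 | 0 |

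**Step 3. Do late fatal SAEs reach the tables?** Protocol 9.2.2 routes SAEs through the eCRF, and its required reporting period is described after the fatal-SAE sentence, so late fatal SAEs fall inside it. SAP 9.2 takes all eCRF data into the analysis. No SAP rule removes them afterwards. This is an inference from three sections, but nothing in the documents points the other way.

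**Step 4. Which outputs mix windows?**
- All-AE, serious and special-interest tables, and preferred-term risk differences: fatal and non-fatal events share a row, so they mix.
- Fatal-AE table: every entry is fatal and every subject is covered to end of participation. There is one window, but off-treatment deaths carry the treatment-emergent label.
- Adjudicated events: SAP 6.3 and 10.6.2 set explicit on-treatment (last dose + 84 days) and on-study windows. Not affected.

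**Step 5. Illustration of scale.** The documents give no rate of early IP stopping and no mortality rate. Assume the last dose is equally likely at each of the 24 visits from Week 1 to Week 93, all stoppers are followed to Day 701, and annual mortality off IP is m = 5% to 20%. The mean stretch is (672 + 28)/2 = 350 days. Averaging 1 − exp(−m × days/365.25) over the 24 visits gives 4.64% (m = 5%), 9.01% (10%) and 16.97% (20%).
- If 20% of 375 stop early (75 subjects): 3.5, 6.8 and 12.7 subjects per arm die in the stretch.
- If 40% stop early (150 subjects): 7.0, 13.5 and 25.5.

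The 20% borrows the sample-size drop-out allowance as a stand-in for IP stopping. These are upper limits on added counts: SAP 6.3 counts a subject once per event, so a subject already in a row adds nothing.

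**The case against.** A reader might go further and infer that the arm whose subjects stop earlier picks up spurious deaths, so that unequal stopping alone creates a difference in fatal treatment-emergent AEs. The documents do not support this. Fatal SAEs are reported to end of participation for everyone, on or off IP. With equal mortality and full follow-up, both arms are counted over the same 700 days, and a death on Day 600 counts either way. The gap arises only if fatal events are cut at 28 days after the last dose. Under the Step 5 assumptions, an arm with 10 points more early stopping would then lose 0.10 × 4.64% = 0.5 to 0.10 × 16.97% = 1.7 points of fatal events relative to the other. The fix has to allow for that.

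Nor do the documents support a claim of inflated fatality, since no case-fatality ratio is planned.

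Three further points count against the concern.
- Late non-fatal SAEs that the investigator learns of must still be reported, though Protocol 9.2.2 places them in the safety database for expedited reporting.
- Stroke, myocardial infarction, decompensated heart failure and thromboembolism, fatal or not, are collected and adjudicated to end of study. Off-treatment survivors of these events are on record, though not necessarily in the AE tables.
- The AE tables are descriptive, and the adjudicated analyses carry the main mortality and cardiovascular comparison.

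All of this limits the reach of the point. It does not supply the missing end date or make the combined rows refer to one period.

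**Conclusion.** The gap is real but confined. As written, late events enter the combined AE and SAE rows, and their risk differences, according to whether they were fatal. Only subjects who stop IP early and remain on study are affected. For them the fatal-only stretch runs from 28 days (last dose at Week 93) to 672 days (a single dose on Day 1). These lengths follow from the documents' calendar; any count of events rests on assumed stopping and mortality rates.

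Mixed windows and the misleading label do not need the arms to differ. A distortion between arms in the combined rows would need different rates or timing of stopping, which the documents do not predict, although Protocol 10.5.2.1 and SAP 10.5.1 allow for differential follow-up on the primary endpoint. The primary efficacy analysis is not touched. The definition should be corrected before unblinding because it is cheap to do and the rows will be read as on-treatment safety.

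**What to change.** - In SAP 6.3, define treatment-emergent once as onset from the first dose through 28 days after the last dose, and have 10.6.1 refer to it. This matches the AE collection period and the 28 days in the SAP's IP-exposure definition. It also settles the small difference between the two start rules and handles stray late non-fatal reports.
- Use it for every table and risk difference that combines fatal and non-fatal events. An event with onset inside the window and a later death stays counted.
- Report fatal AEs by arm both within that window and through end of study, with later-onset fatal events shown separately.
- Add a footnote that the 28-day AE window differs from the 84-day on-treatment window for adjudicated events. A death 50 days after the last dose would be outside the first and inside the second.
- State that fatal events limited to 28 days depend on time on IP, so the comparison of mortality between arms rests on the on-study analysis.

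Cost: SAP wording, a footnote and one additional table. No event is lost from the report, and no change to data collection is needed.
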